#### 9.4.3 ANALYSIS OF THE SECONDARY ENDPOINT(S)

N/A

---

#### 9.4.4 SAFETY ANALYSES

N/A

---

#### 9.4.5 BASELINE DESCRIPTIVE STATISTICS

N/A

---

#### 9.4.6 PLANNED INTERIM ANALYSES

N/A

#### 9.4.7 SUB-GROUP ANALYSES

N/A

#### 9.4.8 TABULATION OF INDIVIDUAL PARTICIPANT DATA

We will report individual participant data in terms of their pre- and post- stimulation values for both the active and sham stimulation condition for primary outcomes.

#### 9.4.9 EXPLORATORY ANALYSES

Exploratory analyses we may pursue include testing whether stimulation targeting predicts individual differences in the strength of stimulation effects. We will pursue this question through E-field modeling – a method which estimates the strength of local stimulation based on the actual coil placement and individual participants' brain morphology. We may also ask whether the area in which actual stimulation intensity was the strongest lies within functional connectivity network parcellations and whether that relates to the strength of stimulation effects on behavior.

### 10 SUPPORTING DOCUMENTATION AND OPERATIONAL CONSIDERATIONS

#### 10.1 REGULATORY, ETHICAL, AND STUDY OVERSIGHT CONSIDERATIONS

##### 10.1.1 INFORMED CONSENT PROCESS

###### 10.1.1.1 CONSENT/ASSENT AND OTHER INFORMATIONAL DOCUMENTS PROVIDED TO PARTICIPANTS

Consent forms describing in detail the study intervention, study procedures, and risks will be given to the participant and written documentation of informed consent will be completed prior to starting the study intervention.

###### 10.1.1.2 CONSENT PROCEDURES AND DOCUMENTATION

In a private room, participants will be given a verbal description of basic study procedures and asked if they have any questions. Next, participants will be given the Informed Consent Document and instructed to read through it carefully, taking as much time as they need, and asking any questions that arise. Finally, if participants and the experimenter are satisfied with the participants' understanding of the procedures, participants will be instructed to sign to indicate their consent to participate.

We are only recruiting fluent English speakers for this study and there is no need to plan for obtaining consent from those who do not speak English. Likewise, as we are only recruiting healthy young adult participants, there is no need to plan for special accommodation to obtain consent for those who are unable to consent on their own behalf.

---

#### 10.1.2 STUDY DISCONTINUATION AND CLOSURE

This study may be temporarily suspended or prematurely terminated if there is sufficient reasonable cause. Written notification, documenting the reason for study suspension or termination, will be provided by the suspending or terminating party to study participants, the funding agency, and regulatory authorities. If the study is prematurely terminated or suspended, the Principal Investigator (PI) will promptly inform study participants, the Institutional Review Board (IRB), and sponsor/funding agency and will provide the reason(s) for the termination or suspension. Study participants will be contacted, as applicable, and be informed of changes to study visit schedule.

Circumstances that may warrant termination or suspension include, but are not limited to:

- Determination of unexpected, significant, or unacceptable risk to participants
- Insufficient compliance of study staff to the protocol (i.e., significant protocol violations)
- Data that are not sufficiently complete and/or evaluable

The study may resume once concerns about safety, protocol compliance, and data quality are addressed, and satisfy the funding agency, sponsor, IRB, Food and Drug Administration (FDA), or other relevant regulatory or oversight bodies (OHRP).

---

#### 10.1.3 CONFIDENTIALITY AND PRIVACY

Participant confidentiality and privacy is strictly held in trust by the participating investigators, their staff, the safety and oversight monitor(s), and the sponsor(s) and funding agency. This confidentiality is

extended to the data being collected as part of this study. Data that could be used to identify a specific study participant will be held in strict confidence within the research team. No personally-identifiable information from the study will be released to any unauthorized third party without prior written approval of the sponsor/funding agency.

All research activities will be conducted in as private a setting as possible.

The study monitor, other authorized representatives of the sponsor or funding agency, representatives of the Institutional Review Board (IRB), regulatory agencies or representatives from companies or organizations supplying the product, may inspect all documents and records required to be maintained by the investigator. The study site will permit access to such records.

The study participant's contact information will be securely stored at each site for internal use during the study. At the end of the study, all records will continue to be kept in a secure location for as long a period as dictated by the reviewing IRB, Institutional policies, or sponsor/funding agency requirements.

Study participant research data, which is for purposes of statistical analysis and scientific reporting, will be transmitted to and stored on secure, password protected University-run data servers which are only accessible to lab members. This will not include participants' contact or identifying information. Rather, individual participants and their research data will be identified by a unique study identification number. The study data entry and study management systems used by sites and by research staff will be secured and password protected. At the end of the study, all study databases will be de-identified and archived digitally.

Although age and sex will be collected, these data are insufficient to identify participants.

Participants' identities will not be conveyed to any third parties.

#### Measures Taken to Ensure Confidentiality of Data Shared per the NIH Data Sharing Policies

It is NIH policy that the results and accomplishments of the activities that it funds should be made available to the public (see <https://grants.nih.gov/policy/sharing.htm>). The PI will ensure all mechanisms used to share data will include proper plans and safeguards for the protection of privacy, confidentiality, and security for data dissemination and reuse (e.g., all data will be thoroughly de-identified and will not be traceable to a specific study participant). Plans for archiving and long-term preservation of the data will be implemented, as appropriate.

### Certificate of Confidentiality

To further protect the privacy of study participants, the Secretary, Health and Human Services (HHS), has issued a Certificate of Confidentiality (CoC) to all researchers engaged in biomedical, behavioral, clinical or other human subjects research funded wholly or in part by the federal government. Recipients of NIH funding for human subjects research are required to protect identifiable research information from forced disclosure per the terms of the NIH Policy (see <https://humansubjects.nih.gov/coc/index>). As set forth in 45 CFR Part 75.303(a) and NIHGPS Chapter 8.3, recipients conducting NIH-supported research covered by this Policy are required to establish and maintain effective internal controls (e.g., policies and procedures) that provide reasonable assurance that the award is managed in compliance with Federal statutes, regulations, and the terms and conditions of award. It is the NIH policy that investigators and others who have access to research records will not disclose identifying information except when the participant consents or in certain instances when federal, state, or local law or regulation requires disclosure. NIH expects investigators to inform research participants of the protections and the limits to protections provided by a Certificate issued by this Policy.

---

#### 10.1.4 FUTURE USE OF STORED SPECIMENS AND DATA

Data collected for this study will be analyzed and stored on password-protected research-dedicated servers at Rutgers University. After the study is completed, the de-identified, archived data will be transmitted to and stored at the RUresearch Data Portal hosted by Rutgers University, for use by other researchers including those outside of the study. When the study is completed, access to study data will be provided through the RUresearch Data Portal.

---

#### 10.1.6 SAFETY OVERSIGHT

##### **Safety Monitoring**

Participants will be monitored for adverse events by study staff. Significant as well as mild adverse effects of TMS stimulation (seizures, headache) and MRI scanning (claustrophobic reaction, and movement of ferromagnetic objects) will be monitored before and after each TMS and MRI session.

##### **Risk mitigation plan and Trial stopping rules**

Three outcomes will be monitored throughout the study as safety endpoints associated with a stop rule.

1. **Number of TMS-induced seizures:** As described above, we will track TMS-induced seizures and clinically significant adverse events requiring outside evaluation. Each stop rule is described in detail below:
  - a. More than 1 TMS-induced seizure resulting in hospitalization within any 10 consecutive participants who receive TMS will result in a protocol hold until further evaluation by the PI. [name] has experience with TMS and overseas safety and training compliance for the Core TMS-EEG facility at Rutgers Center for Advanced Human Brain Imaging Research. No new TMS sessions will be administered to any participant once this stop rule is enacted until evaluation of the events is concluded and it is deemed appropriate to proceed. However, participants who have completed their TMS treatments may be scheduled for follow-up visits.
2. **Clinically significant adverse events (i.e. adverse events that require referral for further evaluation) likely related to TMS.** For example, a mild headache after TMS that resolves spontaneously or with over-the-counter medication will not be considered clinically significant. A severe headache that starts during or shortly after TMS and fails to resolve with time and/or OTC intervention would prompt referral to an Emergency Department and will be considered clinically significant.
  - a. If more than 1 clinically significant adverse event related to TMS administration and having similar clinical features is seen within any 10 consecutive participants, the protocol will be put on hold until further evaluation by the PI. Follow up EEG visits may continue but TMS will not be administered until the hold is resolved.

3. **Adverse events related to MRI:** Risks associated with MRI scanning will be minimized in the following manner. First, subjects will be screened for contraindications to MRI. In particular, subjects will be excluded from the MRI studies who have a history of moderate or severe claustrophobia, or a history or possible history of any intra-ocular, intracranial, intra-thorax, or intra-abdominal metal or cardiac pacemakers. Subjects will be screened twice prior to the study, once at the time of initial contact, and a second time when they arrive at the MRI facility prior to the study. Anxiety will be minimized by thoroughly explaining the procedures and the nature of the magnetic resonance scanner to subjects prior to study. During the scanning procedures, the subjects are continually monitored visually and auditory for any potential problems, and subjects are assured that they can be removed from the scanner at any time if problems should arise or they are experiencing discomfort. Emergency medical equipment and pharmaceuticals are present at all of the MRI facilities to be used in this project. The development of muscle aches and pains is minimized by providing appropriate cushions at pressure points and beneath the knees as desired by the subject. The appearance of claustrophobia on entering the MRI scanner usually results in termination of the experiment. Earphones and/or earplugs will be used to dampen the sound of the MRI procedure (with a minimum 30 dB dampening effect as per FDA guidelines).

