#### Risks associated with participation in TMS experiments:

(1) Heating, induced voltages, and magnetic field effects. The action of the magnetic field on any implanted or worn metal in, on, or around the head poses a significant risk. Magnetic fields can move or dislodge metal, induce current in conductive metals, cause heating around metal components, and/or affect the operation of any metal device. Thus, it is crucial to screen participants for any irremovable metal in or around the head. Our health screening includes the relevant screening questions.

(2) Hearing changes. Movement of the TMS coil within its casing when current is passed through it produces an audible “click”. Though this click is often not perceived as loud due to the stapedial reflex, it can nevertheless reach 140 dB or more of sound pressure. This exceeds OSHA sound level limits and could produce changes in hearing levels if exposed repeatedly. Thus, we will require all participants to wear earplugs. In addition, we will exclude participants with potential hearing problems.

(3) Induced seizure: Though exceedingly rare even in patients with epilepsy, induction of a “generalized” seizure is the most severe adverse event associated with TMS. A seizure is an episode of excessive brain activity and stiff muscle activity (often referred to as a “convulsion” or “fit”). Seizure risk increases at high stimulator output intensities, at high frequencies of stimulation, with multiple repeated trains of

stimulation, with long durations of stimulation, with short inter-train-intervals, and when stimulating participants with reduced seizure thresholds. However, the risk of seizure induction is minimal to negligible if TMS parameters are kept within the prescribed consensus safety parameters (Rossi et al., 2009; Rossi et al. 2020), and participants are carefully screened for seizure risk. Indeed, over the past decade of experience in both clinical and research domains, this risk has been reduced to the order of one 1 in 89,000 cases (Rossi et al 2020).

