### 2.3.2 KNOWN POTENTIAL BENEFITS

The proposed research does not guarantee direct benefits to the participants beyond the opportunity to participate in a scientific enterprise. There is a potential indirect benefit of this research as it may advance understanding of the cognitive control of sequences of tasks, knowledge that may have beneficial clinical or societal impact.

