As noted above, the chief risk of TMS studies is seizure, yet this risk is significantly mitigated by well established, consensus guidelines with a proven track record for safe administration (Rossi et al. 2009; Rossi et al. 2020). Key methods for minimizing seizure risk include screening against risk factors among otherwise healthy young adult participants (e.g. epilepsy, history of brain trauma, the use of anti-depressants, etc.). Additionally, we will adhere closely to safety consensus guidelines as articulated by Rossi et al., which have a proven track record of safe administration. Nevertheless, as we cannot rule out seizure risk entirely, every experiment will be run by the PI ([name]) or highly-trained staff member and a second experimenter trained to respond quickly and effectively in the event of a seizure. All experimenters will be thoroughly trained, and closely familiar with the protocol for responding including securing the participant to preclude further harm, contacting emergency medical services, remaining with and reassuring the participant until emergency medical services arrive, and subsequently documenting and reporting the incident to our IRB.

For MRI, there are no known risks beyond interactions between metal and the magnetic field. Hence, all participants are extensively screened for implanted metal. Persons at primary or secondary risk based on an implanted object or medical device will be excluded according to MRF operating procedures. Moreover, no personnel are permitted in the scanner room with any metal on their person. As such, we do not anticipate any significant risk from the application of these procedures. In rare cases, a participant

will become anxious because of lying in an enclosed space. We will exclude participants who report a history of anxiety in enclosed spaces, and we will terminate the session of a participant who expresses anxiety about lying in the bore.

All participants will be able to stop the session at any time by squeezing a ball held in one hand. The ball activates a buzzer in the control room. There is also an intercom voice link with the control room that allows verbal communication between participant and experimenters.

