### **Reporting Timeframes**

Principal Investigators must report Reportable Events to the HRPP in accordance with the following timeframes:

- Reportable Events that are either life-threatening or have resulted in death must be reported to the HRPP via telephone, or email if phone is not possible, within one business day from the date the PI is notified of or discovers the Reportable Event. The PI must ensure that Research Personnel are trained to report any Reportable Event to the PI promptly upon discovery, and no later than 24 hours following its discovery or occurrence. A Reportable Events Form must be submitted to

the HRPP within 48 hours of the PI's initial verbal or email notification to the HRPP of the Reportable Event.

- Reportable Events that are not life-threatening and have not resulted in death must be reported to the HRPP in writing as soon as possible, and no later than 7 business days from the date the PI is notified of or discovers the Reportable Event.
- Minor Protocol Deviations must be reported to the HRPP in writing at the time of continuing review when continuing review is applicable to the study protocol, and must be reported during any quality assurance/quality improvement assessment by the HRPP. If continuing review is not applicable to the study protocol, the PI must maintain Minor Protocol Deviations as part of the study record and make the study record available upon request to the IRB, HRPP, and/or any federal sponsor or regulatory agency, as applicable.

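### Neither TMS stop rule pauses stimulation after a first TMS-induced seizure, because both need more than one event

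*Protocol*

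**What the plan says.** Section 10.1.6 (Risk mitigation plan and Trial stopping rules) holds two rules on TMS.

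- Rule 1a: "More than 1 TMS-induced seizure resulting in hospitalization within any 10 consecutive participants who receive TMS will result in a protocol hold". The hold stops new TMS sessions for every participant until the events have been evaluated.
- Rule 2a: "If more than 1 clinically significant adverse event related to TMS administration and having similar clinical features is seen within any 10 consecutive participants", a hold likewise follows. Item 2 defines clinically significant events as "adverse events that require referral for further evaluation".

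Section 2.3.1, in its list of TMS risks, states that a generalized "seizure is the most severe adverse event associated with TMS" and that "this risk has been reduced to the order of one 1 in 89,000 cases". The word 'cases' is not defined. Section 2.3.2 says the research "does not guarantee direct benefits to the participants".

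For a single seizure, section 2.3.3 requires an emergency response, including a call to emergency medical services, and "subsequently documenting and reporting the incident to our IRB". Section 8.3.6 makes the investigator evaluate a serious adverse event and report the result to NIH and the IRB within 7 working days. A life-threatening reportable event goes to the HRPP "within one business day from the date the PI is notified of or discovers the Reportable Event" (section 8.3.5). The AE/SAE follow-up plan in 10.1.6 has the investigator judge whether risk against benefit has changed. Halting procedures appears in section 8.4.1 as an example of a corrective action, and section 10.1.2 allows suspension for reasonable cause.

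**The concern.** A stop rule takes the first decision out of the hands of those running the study. Here the rule written for the event that the protocol itself ranks as most severe stays silent on its first occurrence. The participants are healthy volunteers with no promised benefit, so little is lost to them by pausing. The stated risk is also so low that one seizure in this trial would itself be strong evidence against it.

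The time at stake is the interval between the first seizure and the end of its evaluation. In that interval, whether other volunteers keep receiving TMS depends on judgement. Safety oversight is directed by the investigator (section 10.1.6, Data Safety Monitoring), so the choice rests largely with the person running the trial.

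**Working it through.** **Step 1. Compare the triggers.**

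| | Rule 1a | Rule 2a |
|---|---|---|
| Event | TMS-induced seizure | TMS-related event with similar clinical features |
| Severity | hospitalization | referral for further evaluation |
| Count | more than 1 | more than 1 |
| Window | 10 consecutive TMS recipients | 10 consecutive participants |

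Nothing in item 2 excludes seizures. Section 2.3.3 sends any seizure to emergency services, which is at least a referral, and two seizures share clinical features. Two seizures without admission would therefore ordinarily trigger 2a. One seizure, admitted or not, triggers neither rule.

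**Step 2. Inputs.** The protocol states no operating characteristic for either rule, so there is no figure to reproduce. The inputs are:

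- Stated rate p0 = 1/89,000 (section 2.3.1).
- 60 participants (section 9.2).
- Two active sessions each (section 6.3), so 60 × 2 = 120 active sessions.
- Two trains per session (section 6.1.2), so 120 × 2 = 240 active trains.

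Sham exposure is left out because section 6.1.2 says it has no neuronal effect. Since 'case' is undefined, all three denominators are shown. Events are assumed independent.

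**Step 3. Chance of any seizure, and what one seizure would imply.**

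- P(at least 1) = 1 − (1 − p0)^n
- Exact two-sided 95% lower limit after one event in n = 1 − 0.975^(1/n)
- P(at least 2 anywhere in the trial) = 1 − (1 − p0)^n − n·p0·(1 − p0)^(n−1)

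| n | P(at least 1) | Lower limit after 1 event | Multiple of p0 | P(at least 2) |
|---|---|---|---|---|
| 60 participants | 0.067% | 4.22 × 10⁻⁴ | 37.5 | 2.2 × 10⁻⁷ |
| 120 active sessions | 0.13% | 2.11 × 10⁻⁴ | 18.8 | 9.0 × 10⁻⁷ |
| 240 active trains | 0.27% | 1.05 × 10⁻⁴ | 9.4 | 3.6 × 10⁻⁶ |

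For example, with n = 60 the lower limit is 1 − 0.975^(1/60) = 0.000422, and 0.000422 × 89,000 ≈ 37.5. Rule 1a needs at least two seizures, so the last column is an upper bound on its chance of firing at the stated rate.

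**Step 4. How 1a behaves if the stated rate is wrong.** Let r be the rate per active session and p = 1 − (1 − r)² the rate per participant, with at most one counted event each. The chance that two affected participants ever fall within 10 consecutive out of 60 is

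P(1a fires) = 1 − Σₖ C(60 − 9(k − 1), k) pᵏ (1 − p)^(60 − k), where the k = 0 term is (1 − p)^60.

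The rates above 1/89,000 are assumptions, chosen to show the range.

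| r | P(at least 1 seizure) | P(1a fires), all admitted | P(1a fires), half admitted |
|---|---|---|---|
| 1/89,000 | 0.00135 | 2.5 × 10⁻⁷ | 6 × 10⁻⁸ |
| 1/1,000 (89 × p0) | 0.113 | 0.0019 | 0.0005 |
| 1/100 (890 × p0) | 0.70 | 0.15 | 0.04 |

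A simulation at r = 1/100 with all admitted gave 0.148, in agreement with the formula. Under the single-event hold proposed below, the chance of a hold equals the first probability column.

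**The case against.** The strongest defence is that a first seizure is not ignored. If it is classed as serious, section 8.3.6 obliges the investigator to evaluate it and report outside the site. The follow-up plan in 10.1.6 requires a risk-benefit determination. Section 8.3.3.3 lets an event count as unexpected on frequency, which could make it reportable under 8.3.5, and that report must describe any corrective action. Sections 8.4.1 and 10.1.2 give authority to halt. Rule 1a's own hold also ends on the investigator's evaluation. All of this stands. It narrows the gap to whether TMS pauses by rule or by judgement while the review runs, but it does not close it.

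A reader might infer that two seizures without admission would trigger no hold, so that seizures face a stricter bar overall than severe headaches do. The documents do not support this: 1a's wording is stricter, but item 2 carves out no exception for seizures and 2a would ordinarily catch them. On that reading 1a is partly redundant, which is a drafting weakness. A reader might also infer that the response to one seizure is only reporting or optional steps. That is wrong too, since the evaluation of a serious event and the risk-benefit review are duties.

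It is fair to add that the rule is explicit and workable, that no standard in the protocol demands a one-event trigger, and that the rates of 1/1,000 and 1/100 have no basis in the protocol. Judgement also remains under any rewording, because whether a seizure is TMS-induced rests on a clinician's assessment (section 8.3.3.2), made in a double-blind study.

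**Conclusion.** The point holds in a narrow form: neither stop rule pauses TMS for other volunteers after a first TMS-induced seizure. At the stated rate such a seizure has a chance of about 0.07% to 0.27% over the whole trial, so the expected practical impact is small. If one did occur, the 95% lower limit would lie about 9 to 38 times above the stated rate, which is reason enough to pause while the required evaluation is done. Rule 1a adds little protection when the rate is badly wrong: at an assumed 1 in 100 per active session it would fire with probability of only 0.15 even if every seizure led to admission.

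These figures rest on independent events, on seizures arising only from active stimulation, and on the undefined unit 'case' being a participant, a session or a train. The conclusion is the same under all three units. This is a cheap safety improvement, and it does not bear on the trial's efficacy analysis.

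**What to change.** In section 10.1.6, remove the hospitalization condition, the count and the 10-participant window from rule 1a. Restate it along these lines: *Any single TMS-induced seizure places all TMS on temporary hold until the event has been evaluated and resumption is judged appropriate.* The release condition is in substance the one that 1a already has. Keep rule 2a for other clinically significant TMS-related events, which also removes the overlap between the two rules.

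The cost is an IRB-approved wording amendment, with no added procedures or participants. At the stated rate the hold would be used with a chance of about 0.07% to 0.27%. If it were used, some participants between sessions could pass the 4-month completion limit in the synopsis (section 1.1).
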